3.3.1 Noninvasive continuous hemodynamic parameters

After 20 minutes of comfortable rest, in the supine position, humeral blood pressure will be determined according to guidelines.³⁰ Blood pressure measurements will be performed before (baseline) and immediately after vaping sessions or sham-vaping. A cuff will be placed on the middle phalanx of the right middle finger in order to obtain a finger blood pressure waveform with a beat-to-beat hemodynamic monitoring system (Finometer Pro[©], FMS, Amsterdam, the Netherlands).¹⁷ This permitted a continuous monitoring of the humeral systolic and diastolic blood pressures throughout all the experimental sessions duration. Pulse rate will be monitored throughout the study by the finometer recordings. In addition a continuous electrocardiogram monitoring will be performed (AdInstrument[©]).

3.3.2 Continuous respiratory rhythm, end-tidal carbon dioxide and blood oxygen saturation

Continuous, non-invasive, real-time respiratory status monitoring of end-tidal CO₂ pressure, O₂ saturation in arterial blood, respiration rate, and pulse rate will be assessed with the Capnostream 35 monitor[©] (Oridion Medical Ltd, Jerusalem, Israël) throughout all the experimental sessions duration.

3.3.3 transcutaneous oxygen and carbon dioxide partial pressures

A PeriFlux system 5000 (Perimed[©], Järfälla, Sweden) will explore transcutaneous oxygen (O₂) and carbon dioxide (CO₂) partial pressures by means of a PF 5040 unit and a dual transcutaneous O₂ and CO₂ partial pressures E5280 electrode. After wiping the area with alcohol, a TC 550 fixation ring (Perimed[©], Järfälla, Sweden) will be applied to the skin in the medial side of the right arm (lower third and 5 cm distal to the antecubital fossa) at the level of the heart. Four drops of contact liquid (TC 560, Perimed[©], Järfälla, Sweden) will be instilled

inside the TC 550 fixation ring. Avoiding superficial vessels and body hair, the electrode will be placed at the same location for each of the two sessions on the basis of multiples pictures taken during the experimental session. Transcutaneous O₂ and CO₂ partial pressures values will be considered stable when variations did not exceed ± 2 mmHg within 1 min. Electrode remembranring will be done every two sessions.

3.3.4 skin microcirculatory blood flow by means of laser Doppler perfusion monitoring

3.3.4.1 Skin continuous vascular conductance

Skin continuous microcirculatory blood flow will be assessed using a PeriFlow system 5000, PF 5010/5020 with the thermostatic probe 457 (Perimed®, Järfälla, Sweden) at the level of the right arm at least 5 cm from the PF 5040 with combined transcutaneous O₂ and CO₂ - E5280 electrode; and mean arterial pressure will be measured throughout the sessions with a beat-to-beat hemodynamic monitoring system (Finometer Pro, FMS®, Amsterdam, the Netherlands) on the right middle finger.¹⁷ Cutaneous vascular conductance will be then calculated as skin continuous microcirculatory blood flow divided by mean arterial pressure.

3.3.4.2 Evaluation of microvascular reactivity to pharmacological stimulation.

"Endothelium-dependent and -independent vasodilatation of the skin microcirculation (measured in perfusion units, PU= 10 mV) will be noninvasively and continuously evaluated by laser Doppler fluxmetry technique in combination with iontophoresis (Periflux 5001 and Perilont, Perimed, Jarfalla, Sweden) of acetylcholine (ACh), after vaping or sham vaping and iontophoresis of sodium nitroprusside (SNP), minutes after vaping or sham vaping. The laser Doppler flowmetry probes will be constantly heated at throughout the study so as to avoid changes in microvascular blood flow due to local skin temperature variations. Drug-delivery

electrodes (PF 383, Perimed) incorporated into the head of the laser probe (PF 481-1, Perimed), will be carefully placed, by the use of specific double sided skin adhesive patches on the forearms. The drug-delivery electrodes will be filled with 200 μ l ACh dissolved in distilled water and will be attached with the laser probe to a standardized site on the right forearm (anterior and proximal part) that had no visible veins. The dispersive electrode will be attached approximately 15 cm away from the electrophoresis chamber, according to the manufacturer's instructions. A protocol of three fixed doses (current intensity-delivery time) will be employed, resulting in an incremental dose \pm response curve. After measuring the resting flow, three doses of 0.1 ACh dissolved in distilled water will be delivered using a cathodal current (0.1 mA for 80 seconds, with total charges of 8 millicoulombs) at 120-second intervals. The mean values of the resting flow will be considered to be the basal flow values for each patient. Using a new delivery electrode applied on the left forearm, three doses of a solution of SNP dissolved in distilled water will be delivered using an anodal current (0.1 mA for 80 seconds, with total charges of 8 millicoulombs at 120-second intervals). The curves of the microvascular flow increases induced by SNP and Ach will always have a total recording time of 20 minutes: three times 80-second of iontophoresis at 120-second intervals and 10 minutes to reach the plateau response after the last dose. ¹⁸ (CLINICS 2011;66(4):599-605)

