A. In comparison to pursuit of PG/GLY vaping with or without nicotine, e-cigarette cessation for five days:

- Increases transcutaneous O₂ tension and O₂-haemoglobin saturation
- Decreases respiratory rhythm
- Increases lung diffusing capacities and forced expiratory flows
- Increases maximal rate of oxygen consumption during cycle ergospirometer test
- Modifies heart rate variability
- Decreases arterial stiffness
- Decreases serum PG/GLY and nicotine concentrations

B. In comparison to PG/GLY vaping with nicotine, e-cigarette cessation for five days or PG/GLY vaping:

- Increase cutaneous vascular conductance and decrease arterial stiffness
- Increase acetylcholine and heat mediated vasodilation

C. Each of the three experimental sessions (e-cigarette cessation, PG/GLY vaping and pursuit regular consumptions):

- Induces specific serum, urine and exhaled breath condensate metabolomics profiles
- Induces specific serum proteomics profile

This research proposal tests also the following hypothesis regarding acute effects of PG/GLY vaping with and without nicotine in regular e-cigarettes users:

A. In comparison to baseline, PG/GLY vaping without nicotine:

- Decreases transcutaneous O₂ tension and O₂-haemoglobin saturation
- Increases respiratory rhythm
- Increases serum PG/GLY concentrations
- Induces specific serum, urine and exhaled breath condensate metabolomics profiles

B. In comparison to baseline and PG/GLY without nicotine, PG/GLY vaping with nicotine:

- Decreases transcutaneous O₂ tension and O₂-haemoglobin saturation
- Decrease continuous vascular conductance and increase arterial stiffness
- Increases respiratory rhythm
- Increases serum PG/GLY and nicotine concentrations
- Induces specific serum, urine and exhaled breath condensate metabolomics profiles

3. Methodology

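### The printed iontophoresis polarities are opposite to the ionic charges of both test drugs; if followed, the acetylcholine part of secondary Goal B loses sensitivity, so the setting should be verified and the text corrected

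*Combined protocol and SAP*

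**What the plan says.** Section 3.3.4.2 (microvascular reactivity to pharmacological stimulation) sets out to measure "Endothelium-dependent and -independent vasodilatation of the skin microcirculation" by laser Doppler with iontophoresis, using acetylcholine and sodium nitroprusside in turn.

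- **Chamber.** "The drug-delivery electrodes will be filled with" 200 µl of acetylcholine solution. The dispersive electrode is described separately, about 15 cm away.
- **Acetylcholine.** "ACh dissolved in distilled water will be delivered using a cathodal current".
- **Nitroprusside.** With a new delivery electrode on the other forearm, "SNP dissolved in distilled water will be delivered using an anodal current".
- **Dose.** A dose is defined by current and delivery time, with three steps meant to give a dose-response curve. Each step is "0.1 mA for 80 seconds, with total charges of 8 millicoulombs", the same for both drugs.
- **Recording.** "three times 80-second of iontophoresis at 120-second intervals and 10 minutes to reach the plateau response after the last dose", 20 minutes in total.

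The hypothesis that uses the acetylcholine response is in section 2, Goal B of the reversibility hypotheses. It predicts that five days of cessation or of nicotine-free vaping, compared with nicotine vaping, will "Increase acetylcholine and heat mediated vasodilation". Section 3.3.13 names transcutaneous oxygen pressure as the primary objective.

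**The concern.** Iontophoresis works by repulsion: a positive chamber pushes cations into the skin and a negative chamber pushes anions. The printed settings put the cation under the negative electrode and the anion under the positive one. Followed literally, the current would hold each drug back.

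The plan uses charge as its measure of dose, and that holds only if the current carries drug inward. If it does not, the three-step curve is not a dose-response curve for either drug. Nitroprusside is the endothelium-independent comparator and is affected in the same way, so it cannot be used to anchor the acetylcholine reading. No drug-free recording is described that would show the failure while the study was running. A null acetylcholine result could then reflect poor delivery and not unchanged endothelial function.

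**Working it through.** **1. Inputs from section 3.3.4.2.** Current 0.1 mA; pulse 80 s; three pulses per drug; 120 s intervals; 10 min (600 s) after the last pulse; stated charge 8 mC; stated recording 20 min.

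**2. The plan's own figures.**

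- Charge = current × time = 0.1 mA × 80 s = 8 mC per pulse. This reproduces the stated value. Over three pulses: 3 × 8 = 24 mC.
- Recording time = 3 × 80 + 3 × 120 + 600 = 1,200 s = 20 min. This reproduces the stated value if an interval follows every pulse. With only two intervals it is 3 × 80 + 2 × 120 + 600 = 1,080 s = 18 min.

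Neither figure depends on the sign of the current, so their agreement does not confirm or refute the polarity.

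**3. Sign check.** The documents do not state the charge of either drug ion. The charges below follow from what the compounds are: acetylcholine is a quaternary ammonium ion, and sodium nitroprusside is a sodium salt whose active part is the anion.

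| Drug | Charge of drug ion | Chamber sign that drives it into the skin | Printed polarity |
|---|---|---|---|
| Acetylcholine | positive | positive (anodal) | cathodal |
| Nitroprusside | negative | negative (cathodal) | anodal |

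Both rows disagree. The printed polarity belongs to the drug chamber: the text says each drug is delivered with that current from a filled delivery electrode, and it describes the dispersive electrode separately. No other section gives a different polarity.

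**4. What follows for dose.** With the printed signs, raising the cumulative charge from 8 to 16 to 24 mC adds no drug by electromigration. Some drug may still enter passively, but not in proportion to charge.

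**5. Reach.** The polarity rule applies to every iontophoresis recording. Assuming one curve per drug per session and all 21 planned participants completing three sessions, that is 21 × 3 × 2 = 126 curves. Among the hypotheses in section 2, only the acetylcholine half of one Goal B line uses them, and nitroprusside has no hypothesis of its own. The following do not use iontophoresis:

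- the heat test (section 3.3.4.3, a separate probe heated to 44°C);
- vascular conductance (section 3.3.4.1);
- arterial stiffness (section 3.3.6);
- transcutaneous oxygen pressure (section 3.3.3).

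**6. What cannot be calculated.** The documents give no vehicle response, passive diffusion rate or delivered amount. The share of any recorded response due to drug or to current therefore cannot be computed.

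**The case against.** The strongest counter-argument is that this may be a slip in wording and not the setting in use. The section is presented as quoted from a journal article, and exchanging two labels produces exactly this symmetric reversal. The copied text also has gaps in the form available here (a concentration without a unit, a heating temperature and a number of minutes not shown). Whatever their cause, they make it weak evidence of how the current source was set. This stands: the documents cannot tell us which polarity was or will be used. It does not remove the need to act, because the protocol is the instruction that operators follow and the description that readers will rely on.

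A reader might infer something stronger: that the recordings would mostly reflect the current, that the acetylcholine hypothesis could not be tested at all, or that a false positive could arise from the current whatever the state of the endothelium. The documents do not support these readings. The first is a statement of size with no data behind it. The second ignores possible passive entry of drug and holds, if at all, only when the procedure is run as printed. On the third, each participant goes through all three sessions in random order (section 3.1) and Goal B compares sessions. A current effect that is the same in every session would largely cancel in those contrasts, and nothing in the documents suggests that it would differ by session. Loss of sensitivity is the consequence that can be defended.

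The reach is also narrow, as the working shows. That limits the severity but not the defect.

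**Conclusion.** The printed rule is wrong for both drugs. Section 3.3.4.2 assigns each drug chamber the sign that opposes delivery of its ion, and this defeats the section's own definition of dose as current multiplied by time. If followed, the charge steps of 8 mC (24 mC in total) would not represent drug doses. The curves could not be reliably read as endothelium-dependent or endothelium-independent responses, and the acetylcholine part of Goal B would lose sensitivity by an amount that cannot be computed.

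This rests on two assumptions: the ionic charges of the two compounds, which come from their chemistry and not from the documents, and, for the consequences, that the procedure is run as printed. If the practice differs from the text, the recordings are sound in this respect and only the description is in error.

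The point should be fixed. It is confined to a secondary endpoint and does not threaten the primary objective or the sample size.

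**What to change.** 1. Verify the polarity actually set on the current source against the device instructions and the quoted article, before the first session if possible.
2. Correct section 3.3.4.2 so that each drug chamber has the same sign as its drug ion, which means exchanging the words cathodal and anodal.
3. If any session was run at the printed polarity, do not report those recordings as acetylcholine or nitroprusside responses, and say so in the report. If the setting was already the other way round, record that only the text was wrong.

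The cost is two words in the protocol, one check of the device setting and, if needed, a note in the study file. No added procedure, session time or participants are required, and the primary analysis does not change.

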3.3.4.3 Heat test

“Using another laser probe (PF 457, Perimed) at the level of right distal arm (anterior side) that will be positioned at the beginning of the recordings. Maximal skin microvascular vasodilatation will be measured after vaping or sham vaping using prolonged (20 minutes) local heating of the laser probe to 44°C. The use of the area under the blood flow/time curve (AUC) for assessing skin microvascular reactivity using Laser Doppler Perfusion Monitoring is well validated because it represents the global flow response to different physiological and pharmacological stimuli.”³³⁻³⁵ (CLINICS 2011;66(4):599-605)

3.3.5 fractional exhaled carbon dioxide

Fractional exhaled carbon monoxide will be assessed at the start of each experimental session using a Smokerlyzer (SineFuma©, Breda, Holland). Fractional exhaled carbon monoxide should be less than 5 ppm.³⁶

3.3.6 arterial stiffness indices

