3.3 Project plan and various step

The 5h-sessions will take place in the morning at the Hôpital Erasme. During each session, participants will be tested before and after acute exposure at the Cardiology Laboratory (ULB – Pr. [name]) for: 1) noninvasive continuous hemodynamic parameters (Electrocardiogram monitoring (AdInstrument[®]) and a beat-to-beat hemodynamic monitoring system¹⁷ Finapres Medical Systems[®]) 2) continuous respiratory rhythm, end-tidal carbon dioxide and blood oxygen saturation (Capnostream[®]);²⁸ 3) transcutaneous oxygen and carbon dioxide partial pressures (Perimed[®]);¹⁰ 4) skin microcirculatory blood flow by means of laser Doppler perfusion monitoring (continuous vascular conductance, heat test, acetylcholine and sodium nipride iontophoresis) (Perimed[®]);¹⁸ 5) Fractional exhaled carbon monoxide will be assessed at the start of each experimental session using a Smokerlyzer (SineFuma[®], Breda, Holland); 6) arterial stiffness indices (Sphygmocor[®]);²⁹ 7) exhaled breath condensate (Viasys Ecoscreen[®]);¹⁹ 8) Urine and 9) venous blood sample. Then, the participants will be directed to the Laboratory of Exercise Physiology, Faculty of Motor Sciences (ULB – Pr. [name]) to perform assessment of: 10) lung function tests plus capillary and membranous lung diffusing capacity as well as maximal ergometer cycle test²⁰ (details in appendix) (figure 2). After completion of clinical study in all participants, biological samples will undergo proteomics²¹ (ULB – Pr. [name]) and metabolomics²² (UMons – Pr. [name]) analysis (details in appendix).

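### Heat and iontophoresis tests are timed before and after exposure in section 3.3 but only after it in 3.3.4; post-exposure values alone cannot test five-day reversibility of acetylcholine- and heat-mediated vasodilation

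*Combined protocol and SAP*

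**What the plan says.** The timing is given in two places, and they differ.

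- **Section 3.3 (project plan).** The sentence that introduces the list of tests says that "participants will be tested before and after acute exposure at the Cardiology Laboratory". Item 4 of that list is skin blood flow, specified as "continuous vascular conductance, heat test, acetylcholine and sodium nipride iontophoresis".
- **Section 3.3.4.2 (pharmacological stimulation).** Iontophoresis is described as "of acetylcholine (ACh), after vaping or sham vaping", and then "iontophoresis of sodium nitroprusside (SNP), minutes after vaping or sham vaping". No pre-exposure run is described. The resting flow mentioned there is the flow before the drug doses within a recording, not a reactivity test before exposure.
- **Section 3.3.4.3 (heat test).** "Maximal skin microvascular vasodilatation will be measured after vaping or sham vaping using prolonged (20 minutes) local heating". Again no pre-exposure heating is described.

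The hypothesis at issue is item B of the first list in section 2, the list on reversibility. Its comparison is "In comparison to PG/GLY vaping with nicotine, e-cigarette cessation for five days or PG/GLY vaping", and its second line is "Increase acetylcholine and heat mediated vasodilation". Neither response appears in the later list of acute hypotheses.

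Section 3.1 gives sham puffs in the cessation session, nicotine-free puffs in the nicotine-free session and nicotine puffs in the regular consumption session. It promises baseline cardiorespiratory measurements at the start of each session but does not say whether these tests are among them.

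**The concern.** The acetylcholine and heat responses are assigned only to the five-day question. If they are recorded only after the morning's puffs, each value reflects both the preceding five days and an exposure that has just taken place. The two always go together, because the session determines the puffs. Randomising session order or enrolling more participants does not separate them.

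A difference between sessions could then be reported as microvascular recovery over five days when some of it comes from nicotine inhaled that morning. There is also a practical risk: staff who work from 3.3.4 will collect no pre-exposure responses, and these cannot be recovered later.

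**Working it through.** The plan gives no effect size, standard deviation or sample size for these endpoints; section 3.3.13 concerns transcutaneous oxygen pressure only. There is thus no stated figure to reproduce, and the check is one of estimability.

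**Set-up.** For session *c* (C = cessation, N = nicotine-free, R = regular), let *b_c* be the mean response before the session's puffs and *a_c* the change from before to after them.

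- Post-exposure mean in session *c*: *b_c + a_c*.
- Post-exposure contrast, cessation minus regular: (*b_C − b_R*) + (*a_C − a_R*).
- Pre-exposure contrast: *b_C − b_R*.

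The five-day effect is *b_C − b_R*. The nicotine-free comparison has the same form with N in place of C.

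**Estimability.**

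- Post-exposure only: 3 cell means for 6 parameters, design rank 3. The sum of the two effects is estimable; *b_C − b_R* alone is not.
- Before and after exposure: 6 cell means, rank 6. *b_C − b_R* is estimable from the pre-exposure values.

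The post-exposure contrast equals the five-day effect only if *a_C = a_R*. The plan gives no ground for assuming this: its acute item B expects nicotine puffs to lower skin vascular conductance, although it predicts nothing for the acetylcholine or heat response.

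**Illustration under assumption only.** Suppose the five-day effect is zero and the acute difference is 0.25, 0.5 or 0.75 of the standard deviation of the within-person difference. A two-sided paired t-test at 0.05 has n − 1 degrees of freedom and noncentrality d√n; for d = 0.5 and n = 21 this is 0.5 × √21 = 2.29. The chance of declaring a five-day effect is:

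- n = 21: 19.4%, 58.7%, 90.5%
- n = 16: 15.5%, 46.5%, 80.1%

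The nominal rate is 5%. The three values of d are assumptions, not estimates for this trial.

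**Time needed for pre-exposure tests.** Section 3.3.4.2 gives 20 minutes per iontophoresis recording. This is reproduced if an interval follows each dose: 3 × 80 s + 3 × 120 s + 600 s = 1,200 s = 20 min. The heat test is also 20 minutes. Section 3.3 lists three tests, so a pre-exposure set takes 3 × 20 = 60 minutes if run one after another, within a 5-hour session. The documents do not say whether the tests can overlap.

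**The case against.** The strongest reply is that the introductory sentence in 3.3 is loose. It covers exhaled carbon monoxide too, which is taken only at session start, so its before-and-after timing does not fit every item. The two detailed sections agree with each other, and post-exposure only may be what was meant. This stands as an account of intention, but it does not resolve the point. Exhaled carbon monoxide carries its own timing in the list and item 4 does not. If post-exposure only is the intention, that is the case in which the problem arises.

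A second reply is that the comparator in item B carries no duration, and that continued use compared with cessation may properly include the morning's puffs. That is a legitimate estimand. It is not the one announced, because the list is introduced as a test of reversibility.

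A reader might also infer more than the documents support:

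- **That the whole of item B is compromised.** Its other line, on conductance and arterial stiffness, has at least some pre-exposure data: skin flow and arterial pressure are recorded through the session, and augmentation index is taken ten minutes before exposure.
- **That nitroprusside is affected as a hypothesis endpoint.** It shares the timing conflict, but item B does not name it.
- **That the observed difference would be wholly acute.** This is true by definition if the five-day effect is zero. It says nothing about whether that effect is zero.

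**Conclusion.** The conflict between 3.3 and 3.3.4 is in the current text, and nothing else in the document settles it. The consequence is conditional. If the tests are run only after exposure, the acetylcholine and heat comparison estimates the five-day effect plus the same-morning effect and cannot support a claim of five-day reversibility. If they are also run before exposure and those values are used, the mixing with the session's puffs disappears.

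The size of the bias cannot be stated from the documents. The point concerns one line of a secondary hypothesis, not the primary transcutaneous oxygen objective, and it changes no sample size. It should be corrected before data are collected under 3.3.4 as written. The conclusion rests on puff type being fixed by session, which section 3.1 states, and on the section 2 heading being meant as a claim about reversibility.

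**What to change.** Reconcile section 3.3 with 3.3.4.2 and 3.3.4.3, and state which time point tests the acetylcholine and heat line of item B.

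- **If the pre-exposure tests in 3.3 stand:** add them to 3.3.4.2 and 3.3.4.3 and name the pre-exposure acetylcholine and heat responses as the endpoint for this line. First confirm that the three recordings of about 20 minutes each fit before exposure in the 5-hour session, and that a prior test at the same skin site does not alter the post-exposure one. The cost is up to about an hour of session time, which 3.3 as written already implies.
- **If the tests stay post-exposure only:** reword the line as the combined effect of five days plus that morning's exposure, and do not interpret it as reversibility. The cost is a change of wording and a narrower claim.

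Neither route calls for an acute contrast adjusted for the sham change. The plan poses no acute hypothesis for these responses. Sham puffs are given only after five days of cessation, so such a contrast would compare changes measured under different five-day states.
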